#### LDH

- o Grade 1 if >ULN to  $\leq 2xULN$
- o Grade 2 if >2xULN to  $\leq 3xULN$
- o Grade 3 if >3xULN

<sup>2 Uric acid increases will be graded only as Grade 1 or Grade 4. Grade 2 is not defined per CTCAE v4 and Grade 3 cannot be distinguished from Grade 1 based upon the result alone.

#### UPCR

```
 \begin{array}{lll} \circ & \text{Grade 1 if } \geq 17.0 \text{ to} \leq 121.0 \text{ mg/mmol} & (\geq 0.15 \text{ to} \leq 1.0 \text{ mg/mg}) \\ \circ & \text{Grade 2 if } \geq 121.0 \text{ to} \leq 396.0 \text{ mg/mmol} & (\geq 1.0 \text{ to} \leq 3.5 \text{ mg/mg}) \\ \circ & \text{Grade 3 if } \geq 396.0 \text{ mg/mmol} & (\geq 3.5 \text{ mg/mg}) \\ \end{array}
```

# 8.3.2 Analysis

All laboratory data parameters and visits will include flags for values above or below laboratory reference ranges. Toxicity grades will be assigned programmatically by applying the CTCAE v4 guidelines. Only results with assessment dates through the end of the safety observation period (see section 4.5) will be tabulated in summary tables.

Laboratory summaries will be presented in SI units. Continuous laboratory test results will be summarized by treatment group using descriptive statistics for actual values and for changes from baseline by scheduled visit. Box-Whiskers plots may also be presented at each scheduled visit (with visits shown on x-axis) for some laboratory parameters. For continuous laboratory test results which are below or above the quantification level, the imputed values as described in Appendix C will be used for deriving the grade and then summarized.

Tables summarizing the incidence of laboratory abnormalities by maximum post-baseline CTCAE grade overall and by baseline grade will be presented. In addition, the following summaries will also be presented:

AlLiver function abnormalities will be assessed as follows:

- Shift from baseline based on normal ranges
- Summaries of subjects meeting Hy's Law laboratory screening criteria as shown below:

```
    >3× ULN (ALT or AST), >2× ULN Total Bilirubin, and <2× ULN ALP

    >3× ULN (ALT or AST), >2× ULN Total Bilirubin, and ≥2× ULN ALP
```

- Sponsor-defined liver function test surveillance criterion:
  - >10× ULN (ALT or AST) and >2× ULN Total Bilirubin
- B] For renal failure surveillance, a summary of subjects meeting renal failure laboratory screening criteria as shown below will be provided:
  - Serum creatinine >= 3.0xULN and >= 2.0x baseline value or
  - eGFR  $\leq$  50% of the baseline value or

- eGFR < 30 mL/min/1.73 m² and ≥ 25% reduction from the baseline value eGFR = 186 x (Creatinine in mmol per L / 88.4)-1.154 x (Age)-0.203 x (0.742 if female) x (1.210 if black) [from the UK CKD eGuide on the Renal Association website: http://egfrcalc.renal.org/]
- C] Categorical summaries for baseline status for TSH and Free T4 will be presented. In addition categorical summaries for post-baseline TSH and Free T4 status among subjects with TSH and Free T4 in the normal range at baseline will also be presented.

For descriptive summaries for change from baseline analyses, only central lab results will be considered. For analyses of shift in grade from baseline or worst grade after baseline, all available results will be considered regardless of whether from the central or local lab.

Summary Type	Include central lab results?	Include local lab results?
Subject-Incidence of Treatment Emergent Laboratory		
Abnormalities in Selected Laboratory Tests by CTCAE		
Grade	Υ	Υ
Change from Baseline in Laboratory Values	Υ	N
Shift from Baseline in Laboratory Values by CTCAE		
Grade	Υ	Υ
Shift from Baseline in Laboratory Values by		
High/Low/Normal	Υ	Υ
Shift from Baseline in Laboratory Values by Sponsor-		
defined Grades	Υ	Υ
Subject-Incidence of Laboratory Abnormalities with a		
Between-Arm Difference of ≥5% (All Grades) or ≥2%		
(Grades 3-4)	Υ	Υ

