**Table 6-7: Management of Treatment-emergent Proteinuria**

Severity of Proteinuria (UPCR)	Action To Be Taken
≤ 1 mg/mg (≤ 113.1 mg/mmol)	
 
No change in study treatment or monitoring
 

> 1 and < 3.5 mg/mg (> 113.1 and <395.9 mg/mmol)	
 
No change in study treatment required
 
Consider confirming with a 24-hour protein excretion within 7 days
 
Repeat UPCR within 7 days and once per week. If UPCR < 1 on 2 consecutive readings, UPCR monitoring can revert to protocol-specific times. (Second reading is confirmatory and can be done within 1 week of first reading.)
 

≥ 3.5 mg/mg (≥ 395.9 mg/mmol)	
 
Hold study treatment pending repeat UPCR within 7 days and/or 24-hour urine protein.
 
If ≥ 3.5 on repeat UPCR, continue to hold study treatment and check UPCR every 7 days. If UPCR decreases to < 2, restart study treatment at a reduced dose and monitoring of urine protein/creatinine should continue weekly until the UPCR decreases to < 1.
 

Nephrotic syndrome	
 
Discontinue study treatment
 

UPCR = Urine Protein Creatinine Ratio

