  - o Total bilirubin in umol/L ( $< 22.23, \ge 22.23 29.07, \ge 29.07$ )
  - o Neutrophil/Lymphocyte ratio ( $< 3, \ge 3$ )

- Albumin and total bilirubin (ALBI) grade derived from calculated ALBI score = [log(Bilirubin in umol/L)\*0.66 (Albumin in g/L)\*0.085]
  - Grade 1: ALBI score  $\leq$  -2.60
  - Grade 2:  $-2.60 < ALBI score \le -1.39$
  - Grade 3: ALBI score > -1.39

For laboratory parameters summarized as baseline characteristics, the most-recent non-missing central or local sample available before the date and time of randomization will be employed. This differs from definition of baseline laboratory values used in safety summaries.

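### The SAP's eGFR formula labels creatinine in mmol/L but divides by the umol/L factor 88.4; applied as printed, the eGFR < 30 renal-failure criterion cannot be met

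*SAP*

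**What the plan says.** SAP 8.3.2, part B, plans a summary of subjects who meet any of three laboratory criteria for renal failure, joined by "or" in the sense that one is enough:

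1. "Serum creatinine >= 3.0xULN and >= 2.0x baseline value or"
2. eGFR at or below "50% of the baseline value or"
3. "eGFR < 30 mL/min/1.73 m² and ≥ 25% reduction from the baseline value"

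The formula follows: "eGFR = 186 x (Creatinine in mmol per L / 88.4"), with exponent -1.154, times age to the power -0.203, "x (0.742 if female) x (1.210 if black"). The same section states "Laboratory summaries will be presented in SI units", without saying which SI unit holds creatinine. Nothing else in the protocol or SAP gives a different creatinine unit for this formula. Elsewhere the SAP does distinguish micromoles: section 5.3 writes "Total bilirubin in umol/L".

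**The concern.** The unit and the divisor do not belong together. The figure 88.4 takes creatinine from umol/L to mg/dL. Applied to a value in mmol/L it leaves the input a factor of 1,000 too small, and the negative exponent turns that into a very large overestimate of eGFR.

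What is at stake is one of the three prespecified renal-failure criteria. The protocol (section 6.7.9) treats proteinuria as an anticipated event for this drug and notes reports of nephrotic syndrome. It also admits subjects with creatinine up to 1.5 times ULN or a calculated clearance as low as 40 mL/min (section 4.2), so some start close enough to 30 for a moderate creatinine rise to take them below it. An empty row for the absolute eGFR criterion in both arms could be read as reassurance when it only reflects the formula.

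**Working it through.** **Step 1: which unit does 88.4 belong to?** The documents answer this themselves. Protocol Table 6-7 equates "≤ 1 mg/mg (≤ 113.1 mg/mmol"), so 1 mmol of creatinine weighs 113.1 mg. Then

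1 mg/dL = 10 mg/L = 10 / 113.1 mmol/L = 0.0884 mmol/L = 88.4 umol/L.

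The printed 88.4 is therefore reproduced, but only as umol/L per mg/dL. The SAP's UPCR grades (section 8.3.1) imply nearly the same weight at two of their cut-points (17.0 / 0.15 = 113.3 and 396.0 / 3.5 = 113.1). The third pairs 1.0 mg/mg with 121.0 mg/mmol; using that instead gives 10 / 121.0 = 0.0826 mmol/L = 82.6 umol/L, which leads to the same conclusion about the unit.

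**Step 2: size of the error.** The input is 1,000 times too small and is raised to -1.154, so eGFR is inflated by 1000^1.154 = 2,897 for every subject.

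**Step 3: an example.** Non-black man aged 64, creatinine 300 umol/L (0.300 mmol/L); age and creatinine are illustrative assumptions. 64^-0.203 = 0.4299, and 186 x 0.4299 = 79.96.

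- Creatinine in umol/L: 79.96 x (300 / 88.4)^-1.154 = 79.96 x 0.2441 = 19.5
- Creatinine in mmol/L, as printed: 79.96 x (0.300 / 88.4)^-1.154 = 79.96 x 707.3 = 56,554

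**Step 4: when would criterion 3 fire?** Setting eGFR = 30 and solving for creatinine in the formula's unit:

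creatinine = 88.4 x (79.96 / 30)^(1/1.154) = 88.4 x 2.338 = 206.7.

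As umol/L that is a plausible value; as mmol/L it is not. From age 18 (black man) to age 100 (non-black woman) the threshold runs from about 305 down to 148. In mmol/L that is 34 to 17 g of creatinine per litre.

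**Step 5: what happens to the other two criteria?** Criterion 1 does not use eGFR. Criterion 2 is a ratio, so the factor of 2,897 cancels: creatinine going from 90 to 200 umol/L gives 39.8% of baseline eGFR in either unit.

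**Step 6: who is lost?** A 25% fall in eGFR needs a creatinine rise of (1 / 0.75)^(1/1.154) = 1.28-fold. A 50% fall needs 2^(1/1.154) = 1.82-fold. Criterion 1 needs at least a 2.0-fold rise. So subjects whose true eGFR is below 30 after a rise between 1.28- and 1.82-fold are caught by criterion 3 alone.

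Example: non-black woman aged 70, creatinine rising from 120 to 180 umol/L (1.5-fold).

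| | Baseline eGFR | Later eGFR | Change | Below 30? |
|---|---|---|---|---|
| Creatinine in umol/L | 40.9 | 25.6 | -37% | Yes, flagged |
| As printed, mmol/L | 118,630 | 74,299 | -37% | No, missed |

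Her rise is too small for criteria 1 and 2, so as printed she is missed by all three.

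**The case against.** The strongest reply is that the sponsor may not have made this error at all. Only one character separates mmol from umol, and text read from the SAP's PDF is damaged in other places: the minus signs in the exposure formulas of section 6.3 and the operator in the ALBI formula of section 5.3 are missing. No micro sign appears in the SAP text, so nothing shows that one would survive there. This cannot be excluded. But the damage seen is mostly lost operators and dashes, no case of an m standing for a micro sign is evident, and section 5.3 has umol/L for bilirubin. A look at the signed document settles it.

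Second, the effect depends on literal use. If the dataset holds creatinine in umol/L and the program uses it unchanged, the output is right and only the label is wrong. If mmol/L values are used, eGFRs in the tens or hundreds of thousands should be noticed by anyone who looks at them. Both statements are fair. However, a summary that only counts subjects meeting the criteria would not display those values, and the SAP is what the programmer is meant to follow.

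Third, the importance is limited. This is a descriptive table; it drives no dosing, stopping or formal comparison. Proteinuria has its own UPCR management and grading, creatinine increases are graded separately by CTCAE, and two of the three criteria are intact. All of this stands. It bounds the consequence without making the printed formula correct.

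**Conclusion.** The formula is wrong as written. Followed literally, it overstates every eGFR about 2,900-fold and makes the criterion of eGFR below 30 with at least a 25% reduction unattainable. Renal-failure surveillance as a whole is not lost: the gap is confined to subjects with true eGFR below 30 after a creatinine rise of about 1.28- to 1.82-fold. How many there would be cannot be estimated from the documents. Efficacy results and Type I error are unaffected.

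This rests on two assumptions: that the signed SAP really reads mmol, and that the program takes creatinine in that unit. If the signed copy shows a micro sign, the point falls. If the program already uses umol/L, only the text needs correcting.

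**What to change.** In SAP 8.3.2 part B, change the creatinine unit in the eGFR formula to umol/L and keep the divisor 88.4. Equivalently, keep mmol/L and use 0.0884, or multiply by 1,000 before dividing by 88.4. Check the creatinine unit in the laboratory dataset and program, and confirm that one hand-worked case reproduces (man aged 64, non-black, 300 umol/L: eGFR 19.5).

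The cost is one unit in the text. SAP 4.8 already provides an addendum route for minor corrections approved before unblinding. No data collection, sample size or efficacy analysis changes.

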# 8.4 Vital Signs

#### 8.4.1 Variables

The following vital signs will be summarized.

- Systolic blood pressure (mmHg)
- Diastolic blood pressure (mmHg)
- Weight

# 8.4.2 Analysis

Summary tables of vital signs and change from baseline for each study visit will be presented. Only results with assessment dates through the end of the safety observation period (see section 4.5) will be considered for the summaries.

Subject-incidence of clinically meaningful vital sign results as shown below will also be presented:

- Subjects who got worse since baseline and met the following blood pressure criteria on 2 or more visits (need not be consecutive) after first dose (JNC criteria were modified to include single measurement per time point when triplicate assessments were unavailable; JAMA 2003:289:2560):
  - o Pre-hypertension: SBP 120-139 mmHg or DBP 80-89 mmHg
  - Stage 1: SBP 140-159 mmHg or DBP 90-99 mmHg
  - $\circ$  Stage 2: (SBP >= 160 mmHg and DBP <120) or DBP 100-119 mmHg
  - $\circ$  Stage 3: DBP >= 120 mmHg
- Proportion of subjects with weight loss  $\geq 10\%$  after first dose

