### **6.7.7 Hypertension**

Hypertension is a common class effect of drugs that inhibit VEGF pathways and has been reported in subjects treated with cabozantinib.

Blood pressure should be monitored in a constant position at each visit (either sitting or supine). Treatment guidelines for hypertension deemed related to blinded study drug are presented in Table 6-6. In general, subjects with known hypertension should be optimally managed prior to study entry. Decisions to decrease or hold the dose of study treatment must be based on BP readings taken by a medical professional and must be confirmed with a second measurement at least 5 minutes following the first measurement. Other than for hypertension requiring immediate therapy, the presence of new or worsened hypertension should be confirmed at a second visit before taking therapeutic action. It is recommended that this second visit occurs within 1 week.

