**Table 6-6: Guidelines for the Management of Treatment-emergent Hypertension**

Criteria for Dose Modification a	Blinded Study Dose Modification
Subjects NOT receiving optimized antihypertensive therapy	
> 150 mm Hg (systolic) and < 160 mm Hg OR > 100 mm Hg (diastolic) and < 110 mm Hg	
 
Optimize antihypertensive treatment by adding new or additional antihypertensive medications and/or increase dose of existing medications.
 
Reduce study treatment by one dose level if optimal antihypertensive therapy (usually to include 3 agents) does not result in BP < 150 mm Hg systolic or < 100 mm Hg diastolic,
 
If subject is symptomatic interrupt study treatment
 

≥ 160 mm Hg (systolic) OR ≥ 110 mm Hg (diastolic)	
 
Reduce study treatment by 1 dose level
 
Add new or additional antihypertensive medications and/or increase dose of existing medications and monitor subject closely for hypotension. If optimized antihypertensive therapy (usually to include 3 agents) does not result in BP < 150 mm Hg systolic or < 100 mm Hg diastolic, study treatment should be dose reduced further or interrupted
 
Study treatment should be dose interrupted if upper limits of BP (≥ 160 mm Hg systolic or ≥ 110 mm Hg diastolic) are sustained and not adequately manageable or if BP is > 180 mm Hg systolic or > 120 mm Hg diastolic or if subject is symptomatic.
 
Restart study treatment at the most tolerable dose and reescalate only if BP falls to and is sustained at < 140 mm Hg systolic and < 90 mm Hg diastolic.
 

Hypertensive emergency b or hypertensive encephalopathy	
 
Discontinue study treatment
 

a The investigator may decide to initiate or adjust antihypertensive treatment at a lower threshold than systolic BP > 150 mm Hg or diastolic BP > 100 mm Hg based on their clinical judgment and assessment of the individual subject.

b Hypertensive emergency is defined as uncontrolled elevated blood pressure with clinical evidence of progressive or impending end-organ damage (ie, myocardial infarction/ischemia, intracranial hemorrhage, cerebral ischemia, pulmonary edema, encephalopathy, kidney damage)

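### The SAP's blood-pressure stage table combines a two-visit rule with capped, overlapping bands, so a severe reading can be counted at no stage and a mixed reading at two

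*SAP*

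**What the plan says.** SAP 8.4.2 plans two blood-pressure outputs. The first is by visit: "Summary tables of vital signs and change from baseline for each study visit will be presented". The second is a subject-incidence table for subjects who worsened from baseline and "met the following blood pressure criteria on 2 or more visits (need not be consecutive) after first dose".

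The criteria are four bands:
- The lowest, capped on both limbs: "Pre-hypertension: SBP 120-139 mmHg or DBP 80-89 mmHg"
- The next, capped in the same way: "Stage 1: SBP 140-159 mmHg or DBP 90-99 mmHg"
- The third, with a cap on diastolic pressure: "Stage 2: (SBP >= 160 mmHg and DBP <120) or DBP 100-119 mmHg"
- The highest, defined by diastolic pressure alone: "Stage 3: DBP >= 120 mmHg"

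The two-visit condition applies to all four. The SAP does not say whether both visits must fall in the same band, which band applies when a reading fits two, or whether unscheduled readings count. Protocol 5.7.3 has vital signs taken at unscheduled visits where possible, so such readings will exist.

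Protocol 6.7.7 describes how high readings are handled. Decisions to lower or hold the dose rest on readings that "must be confirmed with a second measurement at least 5 minutes following the first measurement". New or worsened hypertension is to be confirmed at a second visit, preferably within a week, before action is taken, except where therapy is needed at once. Actions in Table 6-6 include "Reduce study treatment by 1 dose level", added antihypertensive medication, interruption and discontinuation.

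**The concern.** Hypertension is an expected effect of this drug class (Protocol 6.7.7). It was Grade 3 or higher in 14% of the 2410 pooled single-agent subjects (Protocol 1.3.3.1). The incidence table in SAP 8.4.2 is the only planned count of subjects by measured blood-pressure level, so it is where a reader would look to see how many reached each level.

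Two features of the rule work against that use. First, the two-visit condition extends to the most severe band, where one reading already matters and may be acted on at once. Second, the bands are capped: a Stage 3 visit does not count towards Stage 2, and a Stage 2 visit need not count towards Stage 1. A subject whose readings are consistently high but move between bands can therefore be missed, while the 'or' lets one reading sit in two bands.

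**Working it through.** The plan states no figure for this table, so there is nothing to reproduce. The check applies the rule as written to illustrative readings. The readings are assumed; the bands and the two-visit condition come from SAP 8.4.2. Baseline and all other visits are taken as normal (115/75), so every listed reading is worse than baseline.

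**Step 1: classify single readings (SBP/DBP, mm Hg).**
- 190/125: Stage 3 only. SBP is at least 160, but Stage 2 requires DBP below 120 on that limb and DBP 100-119 on the other.
- 170/105, 168/104 and 172/104: Stage 2 only.
- 150/94: Stage 1 only.
- 132/84 and 130/85: pre-hypertension only.
- 165/85: Stage 2 by SBP and pre-hypertension by DBP.
- 150/125: Stage 1 by SBP and Stage 3 by DBP.
- 200/110: Stage 2 only, because Stage 3 has no systolic limb.

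**Step 2: apply the two-visit rule, same band required, and compare with 'at or above' counting.** The third column shows the highest stage reached on two visits.

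| Post-dose visits | SAP table | Two visits at or above | Highest stage, any visit |
|---|---|---|---|
| 190/125 once | none | none | Stage 3 |
| 190/125, 170/105 | none | Stage 2 | Stage 3 |
| 172/104, 150/94, 132/84 | none | Stage 1 | Stage 2 |
| 190/125, then 130/85 four times | pre-hypertension | pre-hypertension | Stage 3 |
| 165/85 twice | pre-hypertension and Stage 2 | Stage 2 | Stage 2 |
| 170/105, 168/104 | Stage 2 | Stage 2 | Stage 2 |

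The first four rows understate severity in the SAP table, the fifth counts the subject under two separate bands, and the last is counted correctly. Cumulative counting repairs rows two and three. Rows one and four also need an any-visit row.

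**Step 3: try the looser reading.** If the two visits may fall in different bands, rows two and three qualify, but the SAP does not say at which stage to tabulate them. Row one still fails, because there is only one qualifying visit.

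**Step 4: compare with the SAP's other safety summaries.** Laboratory results use the maximum post-baseline grade (8.3.2). ECOG uses the worst value after treatment starts (8.5). QTc above 500 ms (8.6) and weight loss of 10% or more (8.4.2) carry no repeat-visit condition. Blood pressure is the exception, with no worst-value row.

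**Step 5: look at the closing window.** For a subject who stops treatment, the safety observation period ends no later than 30 days after the decision (SAP 4.5). The post-treatment visit falls 30 (+14) days after it (Protocol 5.5.1), so a visit on days 31 to 44 cannot supply the second reading.

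**The case against.** The strongest defence is that a repeat-visit rule is a deliberate choice for specificity. It filters isolated readings and resembles the protocol's own default of confirming at a second visit before acting. Where that happens and both visits share a band, the subject is counted. This stands, and it is a good reason to keep the two-visit count. It does not explain why a Stage 3 visit should not support a Stage 2 count.

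A reader might infer that treated rises generally drop out. The documents do not support that. Those lost are rises acted on at once that do not recur in the band, rises split across bands, and rises with no second reading inside the window.

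It is also fair that other outputs remain. By-visit summaries include the maximum (SAP section 4), so an extreme scheduled reading is visible, although affected subjects are not counted. Treatment-emergent adverse events are tabulated by worst grade and by effect on dosing (SAP 8.1), with no two-visit rule. That route depends on investigator reporting: Protocol 8.1 refers to Section 8.3 for when abnormal vital signs become adverse events, and Section 8.3 gives such criteria only for laboratory data.

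Finally, the same-band requirement is an interpretation. That too stands, but two programmers could then produce different tables from the same text, which is itself a reason to clarify.

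**Conclusion.** The point holds as a defect in one counting rule. On the same-band reading the table omits or misplaces some severe readings and duplicates some mixed ones. On either reading it omits a lone visit with DBP of 120 or more. The effect is limited to one descriptive table; SAP section 8 plans no formal safety comparison, and no efficacy conclusion depends on it.

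Two stronger inferences should not be drawn.

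*That a stated share of affected subjects is missed.* Any such percentage needs a per-visit probability of a high reading, which the documents do not give, and an assumption about correlation between a subject's visits.

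*That the rule shrinks the difference between arms.* Assume seven independent post-dose visits with per-visit probability p. Then P(at least one) = 1 - (1-p)^7, and P(at least two) = 1 - (1-p)^7 - 7p(1-p)^6.

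| p | At least one visit | At least two visits |
|---|---|---|
| 0.05 | 30.2% | 4.4% |
| 0.10 | 52.2% | 15.0% |
| 0.30 | 91.8% | 67.1% |

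At 10% versus 5% per visit, the arm difference falls from 22.0 points to about 10.5. At 30% versus 10%, it rises from 39.6 to 52.1. The direction depends on rates that are unknown, so none can be claimed.

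**What to change.** In SAP 8.4.2:
1. Assign each visit its single highest stage.
2. Count a subject in a stage when two or more post-dose visits are at or above that stage and worse than baseline.
3. Beside this count, add worst-post-dose rows (any single visit) for Stage 2 or above and for Stage 3.
4. State whether unscheduled readings count.

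The cost is revised wording and extra rows in a table shell, approved before unblinding as SAP 4.8 requires; the data are already collected. The small downside is that single-visit rows are noisier and give higher rates in both arms, which is why the two-visit count should stay alongside. The change concerns reporting only and leaves the protocol's management of hypertension untouched.
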